
The investigator team will be notified by the MICU attending after each participant enrollment, so one of the team members will present to MICU to collect the data prospectively in a standardized Data Collecting Sheet (DCS) by using REDCap and all protected health information (PHI) will be de-identified. As regards the control group, an E-research request will be submitted to provide a list by

all the consecutive adult patients admitted to FV-MICU with a diagnosis of DKA in the period between January 1st 2019 till the date of IRB approval. Prespecified sample size and matched in basal patient characteristics and DKA severity will be selected as the control group. Data will be collected retrospectively for the control group and will be recorded directly into the DCS in RedCap. Clinical outcomes will be compared between the intervention and control groups. The primary outcome includes time to anion gap closure ($AG \leq 12$). Secondary outcomes include hospital Length Of Stay (LOS), ICU LOS, total IVII dose, the incidence of transitional failure (defined recurrence of DKA after initial IVII discontinuation within 24 hours and requiring reinitiating the IVII), the incidence of hyperglycemia (> 180 mg/dL) and hypoglycemia (defined as ≤ 70 mg/dL, <54 , <40) during 24 hours from Insulin Glargine administration.

B. Definition of main exposures and outcomes:

Diagnosis of DKA will be made by ICD-10-CM code E10.10, E11.10, or meeting the ADA definition; $BG \geq 250$ mg/dl, $AG > 12$, and positive Ketones in serum or urine

DKA classification as the following table from ADA:

	Mild (plasma glucose >250 mg/dl)	Moderate (plasma glucose >250 mg/dl)	Severe (plasma glucose >250 mg/dl)
Arterial pH	7.25–7.30	7.00 to <7.24	<7.00
Serum bicarbonate (mEq/l)	15–18	10 to <15	<10

For the hyperglycemia analysis, patients will be compared in the following categories according to their mean or median (depending on the normality of the data distribution) blood glucose throughout the hospital stay:

- Mean/median BG <80 mg/dL
- Mean/median BG 81-100 mg/dL
- Mean/median BG 101-140 mg/dL
- Mean/median BG 141-180 mg/dL
- Mean/median BG > 180 mg/dL'
- Mean/median BG > 240 mg/dL

Hypoglycemia will be defined by three categories:

- any glucose level below 70 mg/dL
- any glucose level less than 54 mg/dL
- any glucose level less than 40 mg/dL

For Time of Anion Gap Closure (TAGC) will use the ADA definition: $AG \leq 12$ mEq/L

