Transitional failure will be defined as the recurrence of DKA ($BG \geq 250$ mg/dl, $AG > 12$, and positive Ketones in serum or urine) after initial IVII discontinuation within 24 hours and requiring reinitiating the IVII.

C. Study Population

Intervention vs Control group

- Intervention group: All consecutive adult patients getting admitted to FV- MICU and meet the inclusion criteria and accepted to receive insulin glargine early as per the protocol. They will receive insulin glargine 0.4 unit/kg within 4 hours from initiating the IV Insulin Infusion, as per the Cleveland Clinic DKA protocol.
- Control group: prespecified and matched sample size, consecutive adults who admitted to FV-MICU with a diagnosis of DKA in the period between January 1st 2019 till the IRB approval date and didn't receive basal insulin before AG closure.

Inclusion criteria:

- Age \geq 18 years old
- Meet DKA definition as above
- Having the capacity to sign Informed consent

Exclusion Criteria

- IV insulin infusion initiated more than 4 hours.
- Persistent hypotension (SBP<80 mmHg despite receiving 1000cc normal saline).
- Require Vasopressor
- Acute Coronary Syndrome
- Pregnant
- End-stage renal disease
- Unwilling to consent to participate in the trial
- Currently under police custody
- Transferred from another hospital
- Require emergent surgery
- Alcoholic Ketoacidosis

Study Variables:

General Informations:

- Patient name
- MRN
- Age
- Sex (Male, Female, Others)
- Race (White, Black, Asian, Other)
- Ethnicity (Hispanic vs. Non-Hispanic)
- Weight on admission (kg)
- BMI (Kg/m²)
- Height (cm)
- Date of Hospital admission
- Date of ICU admission

- Date of DKA diagnosis (MM/DD/YY)
- Precipitating cause of DKA
 - Noncompliance
 - New-onset
 - Infection
 - Cerebrovascular accident
 - alcohol abuse
 - pancreatitis
 - Drugs
 - Others

Past Medical history

- Type of diabetes:
 - Type 1 DM
 - Type 2 DM
 - Cystic fibrosis-related diabetes
 - Steroid-induced diabetes
 - Other or no clear diagnosis
- Known diagnosis of other major medical comorbidities (CAD, CHF, HTN, COPD, asthma, liver disease, CKD, cancer, other)
- On Renal Replacement Therapy (Y/N)
- Using Basal insulin at home (Yes/No/ unknown)
- If previous point answer is yes check the corresponding insulin type and write the dose: (Glargine, Detemir, Degludec, NPH, Continuous Insulin Pump) (dose: IU)
- Home total basal insulin dose (units)

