The sample size calculation considered the average time of AG closure in the last 3 months in FV-MICU was 15.6 ± 2.5 hours (CI 95%) and SD of 6 hours. Using one-sided α of 0.025 and an β of 0.10, an expected 20% difference between the two groups, a sample size of 160 totally of the participant will be adequate.

Categorical variables will be described as frequency rates and percentages, and continuous variables will be described using mean, median, and interquartile range (IQR). Proportions for categorical variables will be compared by Chi-squared test of Fisher's exact test. Means for continuous variables will be compared by Student's t-test if normally distributed and Mann-Whitney test if not normally distributed. All statistical analyses will be performed with a one-sided p-value < 0.025 to determine statistical significance. All statistical analyses will be completed by study investigators using Statistical Analysis Software (SAS).

VI. DATA AND SAFETY MONITORING PLAN (if applicable)

All data will be stored in a secured REDcap database. No PHI will be saved on non-HIPAA protected devices. All protected health information (PHI) will be de-identified by using RedCap.

To ensure patient safety, CCF Hypoglycemia protocol is getting followed in all patients receiving insulin including our enrolled participants. Before IV insulin discontinuation, the blood glucose level is getting checked hourly as per protocol. Once the AG is closed and insulin infusion is discontinued, the patient who is maintaining oral intake, blood glucose will be checked with meals, bedtime, and 2 am. If the patient having poor oral intake, blood glucose will be checked q 4 hours. Different treatment options for any hypoglycemic events are available in the protocol depending on the severity of the hypoglycemia event and patient awareness, ranging from oral carbohydrate supplement to IV fluid containing dextrose.

VII. STUDY LIMITATIONS

- Retrospective EPIC data review for the control group. Single-center.

VIII. ETHICAL CONSIDERATIONS

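### Controls are a fixed, matched subset of a full list of past admissions, with no stated selection rule, no safeguard against knowledge of outcomes, and an analysis that ignores the matching

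*Combined protocol and SAP*

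**What the plan says.** Section III.A (Study Design and Methodology) builds the control group in two steps. An electronic request returns "all the consecutive adult patients admitted to FV-MICU with a diagnosis of DKA in the period between January 1st 2019" up to the date of IRB approval. From that list, "Prespecified sample size and matched in basal patient characteristics and DKA severity will be selected as the control group". Then: "Data will be collected retrospectively for the control group and will be recorded directly into the DCS in RedCap".

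Section III.C (Study Population) describes the same group as "prespecified and matched sample size, consecutive adults who admitted to FV-MICU with a diagnosis of DKA", and adds a criterion that applies to controls only: they "didn't receive basal insulin before AG closure".

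Section V (Data Analysis) gives one sample size, 160 for both groups together, and no allocation ratio. Continuous outcomes are compared by Student's t-test or the Mann-Whitney test, with no pairing and no covariates. Section VII lists two limitations: retrospective review for the controls, and a single center.

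The protocol does not name the matching variables, the ratio, a caliper, an algorithm or an order of selection. It does not say who selects, or whether that person works without sight of outcomes.

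**The concern.** This is a non-randomised comparison, so its credibility depends heavily on how the controls are chosen. The controls' times to anion gap closure and lengths of stay are already recorded when the choice is made. Without a reproducible rule, two people working from the same list could produce different control groups and different answers, and a reader could not tell whether the choice was influenced by outcomes.

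The matching also has no counterpart in the analysis. An unpaired, unadjusted test does not use it, and does not correct whatever imbalance it leaves. Part of the stated matching basis is uncertain too: the severity table in section III.B uses arterial pH and bicarbonate, but pH is not among the initial laboratory values listed under Study Variables.

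Finally, if the list holds more eligible patients than are kept, information is left unused that could be had without enrolling or treating anyone further.

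**Working it through.** **Inputs.** From section V: the recent average time to closure "was 15.6 ± 2.5 hours (CI 95%) and SD of 6 hours"; a 20% difference; "Using one-sided α of 0.025 and an β of 0.10"; 160 in total. Not given: the allocation ratio, the size of the list, the IRB date, and the proportion of listed patients who would qualify.

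**Step 1: reproduce the plan's figure.** The difference is 0.20 × 15.6 = 3.12 h. With equal groups, n per group = 2 × 6² × (1.960 + 1.282)² / 3.12² = 77.7, so 78 per group and 156 in total. The t-based calculation gives 78.7, so 79 per group and 158 in total. Both are close to 160, which supports reading the plan as about 80 treated and 80 controls. This remains an inference.

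**Step 2: what a skewed choice of controls could do.** With 80 per group, SE = 6 × √(1/80 + 1/80) = 0.949 h. If there is no true effect but the chosen controls' mean is too long by b hours, the one-sided false-positive rate is 1 − Φ(1.960 − b/0.949):

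- b = 0: 2.5%
- b = 0.5 h: 7.6%
- b = 1 h: 18.3%
- b = 1.5 h: 35.2%
- b = 2 h: 55.9%

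These values of b are illustrations. The documents give no basis for estimating the actual shift.

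**Step 3: what more controls could add.** With 80 treated, SD 6 h, a 3.12 h difference and one-sided 0.025, SE = 6 × √(1/80 + 1/controls). Power is from the t-test:

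- 80 controls: SE 0.949 h, 95% CI half-width 1.86 h, power 90.5%
- 120 controls: SE 0.866 h, half-width 1.70 h, power 94.8%
- 160 controls: SE 0.822 h, half-width 1.61 h, power 96.6%

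These figures count every control fully, before any loss from weighting.

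**Step 4: is a surplus likely?** If ±2.5 h is a 95% half-width with SD 6 h, the three-month sample was about (1.96 × 6 / 2.5)² = 22 patients, or up to about 25 with the t distribution. Assuming a window of 18 to 24 months, the list would hold between 22/3 × 18 = 132 and 25/3 × 24 = 200 admissions before exclusions. Reaching 80 controls would then need 61% (80/132) or 40% (80/200) to qualify. Reaching 120 would need 91% or 60%. Reaching 160 is impossible at the low end and needs 80% at the high end. A surplus over 80 is plausible, but it is not shown.

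**The case against.** Several counter-arguments have force.

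- Matching is a legitimate design, and choosing it over adjustment is not an error. This stands. The gap is that the matching is unspecified and that the analysis ignores it.
- A reader might infer that investigators will choose charts knowing their outcomes. The documents do not say so. Section III.A mentions the list, then selection, then data collection, an order compatible with choosing before outcomes are abstracted. The supportable statement is that nothing prevents outcome-aware selection. The control-only criterion sharpens this, because checking it means reading the chart up to anion gap closure, which is the primary outcome event.
- A reader might infer that the plan certainly discards usable data. Without the pool size and eligibility rate, that cannot be established. Weighting also reduces the effective number of controls: if it halved 160 (an assumption), the precision gain would vanish. Covariate adjustment could work the other way, so the net effect is unknown.
- The terms consecutive and matched need not conflict. In section III.A the first describes the source list and the second the sample drawn from it. Only the wording in section III.C merges them, and it should be clarified.
- Using all controls does not remove selection altogether. Judgement remains on capacity to consent, persistent hypotension and the control-only criterion. Differences in calendar time and consent between the groups also remain.

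**Conclusion.** The point holds as a gap in specification and analysis. A matched subset of past admissions is to be chosen without a stated rule or a safeguard against knowledge of outcomes, and the primary comparison then uses neither the matching nor the baseline data. Following the plan as written can bias the primary result. The documents do not show that it will, or by how much; the rates in step 2 show only that shifts well below the 3.12 h target difference would matter.

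The documents do not support a claim that the study is underpowered: with about 80 per group it meets its own 90% target. Any precision gain is a secondary benefit. It rests on an assumed 1:1 ratio, an unstated pool size and the absence of weighting loss.

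**What to change.** Include as controls every listed admission that meets both the eligibility criteria that can be applied retrospectively and the control-only criterion in section III.C, and state which criteria those are. Make the primary comparison with a regression or propensity-weighted model on named baseline variables already in the data sheet, for example initial anion gap, bicarbonate, glucose, age, weight, diabetes type and home basal insulin. Report counts from the list to the analysed controls, with reasons for exclusion.

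If matching is preferred, fix the variables, ratio and algorithm in advance, run it on a baseline-only extract, lock the control list before outcomes are abstracted, and still adjust the analysis.

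Either route removes discretionary choice among eligible charts. Add the remaining eligibility judgement, and the calendar-time and consent differences, to section VII.

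Using all controls means abstracting additional retrospective charts into the existing REDCap form; how many depends on the pool. It needs no change to the treated group. The matching route costs mainly the advance specification and a separate baseline extract.

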- Non-insulin antihyperglycemics taken at home prior to admission, including the type
 - Sulfonylureas
 - Thiazolidinediones
 - Dipeptidyl peptidase-4 (DPP-4) inhibitors
 - Biguanides
 - Glucagon like peptide-1 (GLP-1) analogues
 - Sodium-glucose transport protein 2 (SGLT2) inhibitors
 - Meglitinides
 - Alpha glucosidase inhibitors
 - Amylin analogues
- History of immunosuppression (history of cancer, HIV or auto-immune disease or organ transplant, chronic steroid)

Initial Laboratory values:

- Anion gap (mEq/L)
- Bicarbonate (mEq/L)
- Glucose (mg/dL)
- Beta-Hydroxybutyrate (mmol/L)
- Ketones in the urine (Y/N/Unknown)
- HbA1c %
- Lactate (mmol/L)

Intervention and outcomes:

- IV insulin infusion starting time
- Insulin glargine administration time
- Anion Gap closure time
- IV insulin discontinuation time
- Number of hours of IVII
- Total IV insulin infusion has been given
- Total IV insulin/weight
- Total IV fluid during DKA management
- Date of discharge from ICU
- Date of discharge from hospital
- Hospital Length Of Stay (days)
- ICU LOS (hours)
- Transitional failure (recurrence of DKA)?

Hypoglycemia Events

- Hypoglycemia event within 24 hrs from glargine
- Time of the hypoglycemia
- How many hours after the glargine administration?
- Severity
- How it has been treated

Hyperglycemia Events

- Hyperglycemia Event after IVII discontinuation by 24 hours (Y/N)
- time of the hyperglycemia event
- Severity of hyperglycemia
- How many hours after IVII discontinuation

D. Outcomes

Primary outcome: Time to anion gap closure (hours).

Secondary outcomes:

- Hospital Length of stay (days)
- ICU length of stay (hours)
- Total IV insulin infusion dose (International unit)
- Incidence of transitional failure (percentage).
- Incidence of hyperglycemia (> 180 mg/dL) during 24 hours from Insulin Glargine administration (percentage).
- Incidence of hypoglycemia (defined as ≤ 70 mg/dL, <54, <40) during 24 hours from Insulin Glargine administration (percentage).

IV. DATA COLLECTION

For the control group, the data will be collected retrospectively and recorded in standardized DCS in RedCap. For the intervention group, the data will be collected prospectively by the investigator team members and observations will be recorded in standardized DCS in RedCap. All protected health information (PHI) will be de-identified for both intervention and control group by using de-identification function in REDCap.

V. DATA ANALYSIS

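### Matching controls on DKA severity is incompletely specified: the severity table needs a pH that is not a listed variable, leaves some eligible patients unclassed, and ignores initial anion gap

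*Combined protocol and SAP*

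**What the plan says.** - **Control selection (III.A).** The intervention group is prospective. Controls come from a list of earlier DKA admissions to the same unit, from which a prespecified number "matched in basal patient characteristics and DKA severity will be selected as the control group". No matching variables, distance or caliper are given.
- **Severity (III.B).** The protocol has one severity scheme, introduced as "DKA classification as the following table from ADA". Its rows are arterial pH (mild 7.25–7.30, moderate 7.00 to <7.24, severe <7.00) and serum bicarbonate in mEq/l (mild 15–18, moderate 10 to <15, severe <10). Every class requires plasma glucose above 250 mg/dl.
- **Eligibility (III.B and III.C).** "Diagnosis of DKA will be made by ICD-10-CM code E10.10, E11.10, or meeting the ADA definition". The laboratory definition is glucose of at least 250 mg/dl, anion gap above 12 and positive ketones. The inclusion criterion is simply "Meet DKA definition as above".
- **Variables (III.C, Initial Laboratory values).** Anion gap, bicarbonate, glucose, beta-hydroxybutyrate, urine ketones, HbA1c and lactate. Neither pH nor a severity class is listed. Section IV has both groups recorded on the same standardized sheet.
- **Analysis (V).** Continuous outcomes are compared by t-test or Mann-Whitney test. No covariate adjustment is planned.

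**The concern.** The comparison is not randomized, and the planned tests take the two groups as they come. Matching is the only stated protection against a difference in how ill the patients were at the start. That matters for time to anion gap closure, because a patient who starts further from the threshold of 12 has further to go. If severity is assigned by an unstated rule, the choice falls to whoever selects the controls, retrospectively, when the closure times are already in the chart. Some eligible patients would have no class to match on. Even a well-assigned class would leave differences in initial anion gap uncontrolled.

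**Working it through.** **The plan's own figure first.** Section V gives a mean of 15.6 h, SD 6 h, a 20% difference, one-sided alpha 0.025 and beta 0.10. The difference is 0.20 × 15.6 = 3.12 h. Per group, n = 2 × (1.960 + 1.282)² × 6² / 3.12² = 77.7, so 78 per group and 156 in total. The t-test version gives 78.7, so 79 per group and 158 in total. The stated 160 is reproduced, with power 90.8% at 80 per group (1:1 allocation is assumed, as no ratio is stated). This point does not change the sample size.

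**Can the table be filled from the listed variables?** The bicarbonate row can. The pH row cannot, as pH is not on the list.

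**Does the table cover everyone who is eligible?** Testing boundary values against the printed classes:

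| Value | Class by that row |
|---|---|
| Bicarbonate 9.9 / 10 / 14.9 / 15 / 18 | severe / moderate / moderate / mild / mild |
| Bicarbonate 18.5, 19, 22 | none |
| pH 6.95 / 7.00 / 7.23 / 7.25 / 7.30 | severe / moderate / moderate / mild / mild |
| pH 7.24, 7.245 | none |
| pH 7.31, 7.35 | none |

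Neither route into the study limits pH or bicarbonate, so values outside the table can occur in eligible patients. As an illustration, take sodium 135, chloride 98 and bicarbonate 20, with the gap computed as sodium minus chloride minus bicarbonate (the protocol gives no formula). The anion gap is 135 − 98 − 20 = 17. With glucose of at least 250 and positive ketones the patient is eligible, yet has no bicarbonate class. Two smaller gaps concern glucose. A value of exactly 250 meets the definition but no class, and a patient entered by diagnosis code may have glucose below 250.

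**What if the two rows disagree?**
- pH 7.26 with bicarbonate 12: mild by pH, moderate by bicarbonate.
- pH 7.10 with bicarbonate 8: moderate by pH, severe by bicarbonate.
- pH 7.32 with bicarbonate 17: no class by pH, mild by bicarbonate.

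The protocol has no rule for any of these.

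**Does a class fix the starting point of the outcome?** No. Holding sodium at 135 and chloride at 98, the moderate band (bicarbonate 10 to <15) runs from a gap of 135 − 98 − 10 = 27 down to just above 135 − 98 − 15 = 22. The fall needed to reach 12 is then 15 at one end of the band and just over 10 at the other. Sodium and chloride also vary between patients, which widens the spread within a class.

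**The case against.** The best defence is that bicarbonate is collected and gives a class to every patient at or below 18 mEq/l with glucose above 250 mg/dl. The protocol asks for matching on severity without saying that the table, or both of its rows, must be used. Absence of pH from the list does not show that it is unavailable. Controls are abstracted from the electronic record, and the Data Collecting Sheet is named as an appendix whose content is not in the text reviewed. The gap at pH 7.24 is a single value if pH is reported to two decimals, and looks like a drafting slip.

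All of this stands, and it rules out three stronger readings.

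- A reader might infer that severity matching cannot be done. It can, on bicarbonate or on continuous values. What is missing is the rule.
- A reader might infer that severity is the only disease-specific factor to be controlled. The protocol also matches on baseline characteristics, and it lists diabetes type, precipitating cause, home basal insulin and HbA1c. It does not say which of these are used.
- A reader might put a figure on the bias. Suppose severe cases close 5 to 8 h later than mild ones and their share differs by 10 to 15 points. The bias is then 0.10 × 5 = 0.5 h to 0.15 × 8 = 1.2 h, or 16% to 38% of 3.12 h. Neither input is in the documents. The result also describes an imbalance that is assumed from the outset, not the part of it caused by leaving out pH.

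The defence does not supply a class above 18, a rule for discordant values, any use of initial anion gap in the severity classes, or an adjusted analysis.

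**Conclusion.** The point holds as one of incomplete specification. The text establishes four things: pH is not a listed variable, bicarbonate above 18 has no class, discordant values have no rule, and the tests are unadjusted. The table's omission of initial anion gap is equally plain, and it matters because the primary outcome is the time for that same quantity to fall to 12. Severity control in this historical-control comparison is therefore weaker than the already collected data would allow.

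Neither the share of patients affected nor the resulting bias can be computed. The documents give only an overall mean and SD for closure time, with no breakdown by severity and no distribution of pH or bicarbonate. A bicarbonate-only class would probably serve most patients, but that is a judgement the documents cannot confirm. The change is worth making because it is nearly free and can be settled before controls are selected, not because a large bias has been shown.

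**What to change.** - In III.A, name initial anion gap and initial bicarbonate, as continuous values, as the severity variables for matching. State the matching distance or caliper before control closure times are abstracted.
- In V, make the primary comparison a regression of time to closure on group, initial anion gap and initial bicarbonate, on the log scale if times are skewed. Keep the unadjusted test as supportive. The one-sided 0.025 level and the sample size of 160 can stay.
- In III.B, use the three classes for description only. State which row decides the class, and add a category for patients outside the table.
- Optionally, record initial pH where it is already in the chart, marked arterial or venous. The main analysis should not depend on it: the protocol does not mention a blood gas, so pH may be missing for some patients.

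The cost is protocol wording and a little more analysis work. No new test on patients and no change to treatment is involved. These steps do not settle which other baseline characteristics are matched, which the protocol should also list.

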Specific Aim 2: Determine the safety of insulin glargine 0.4 unit/kg early administration within four hours from IV Insulin infusion initiation.

III. METHODS

A. Study Design and Methodology:

This will be a prospective, open-label, intervention cohort study including all consecutive adult patients with Diabetes Ketoacidosis (DKA) getting admitted to Fairview Hospital-Medical Intensive Care Unit (FV-MICU). Screening of patient eligibility and informed consent will be done by the MICU admitting physician once the patient gets admitted to MICU. Participants will be given an overview of the study, including study procedures, and potential risks. Participants will be given adequate time to review the consent form and have opportunities to ask questions. After the informed consent process has been completed and a consent form has been signed, a copy of the consent will be provided to the participant and another copy will be secured in the Principle Investigator office in a locked cabinet. Enrolled participants in the intervention group will receive an Insulin Glargine 0.4 Unit/kg within 4 hours from initiating the IV Insulin Infusion, as per the Cleveland Clinic DKA protocol. The remaining of the management will be following the CC DKA protocol including continuing IVII till Anion Gap Closure ($AG \leq 12$), Basal Metabolic Panel Q 2 hrs, and replacing electrolytes as indicated. After closing the anion gap, the decision for giving more Basal Insulin doses will be left to the treating physician's discretion. For patient safety, Point Of Care (POC) blood glucose will be checked hourly before IVII discontinuation. After IVII discontinuation, the BG will be checked with meals, bedtime and 2 am if the patient maintain good oral intake, if not, the BG will be checked q 4 hrs. Target BG 150 – 200 mg/dl during the DKA management and 140 – 180 mg/dl after DKA resolution as per American Diabetes Association recommendations. In case of any hypoglycemia event, this goal will be achieved by using Dextrose containing fluid or carbohydrate enriched oral intake which will be left to the treating physician discretion depending on patient awareness and severity of hypoglycemia. Also, the pre meals and correctional insulin doses after AG closure will be left to the treating physician's discretion. After AG closure the pre meals and correctional insulin doses will be left to the treating physician's discretion. In case of not closing the AG after 24 hours from the initial Glargine dose, the decision for further Glargine doses will be left to the treating physician's discretion.

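### The DKA definition used for entry can be met by an ICD code alone, so a patient without an open anion gap can be included with no valid primary outcome; the control criteria also need to be stated

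*Combined protocol and SAP*

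**What the plan says.** Section III.B gives two routes to a DKA diagnosis: "Diagnosis of DKA will be made by ICD-10-CM code E10.10, E11.10, or meeting the ADA definition". The ADA route requires glucose of at least 250 mg/dl, AG above 12 and positive ketones. The code route requires none of these. The inclusion list in III.C takes the definition over unchanged ("Meet DKA definition as above"), and no other inclusion or exclusion item asks for an open gap.

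The primary outcome is time to AG closure in hours (III.D). For the threshold, III.B states: "For Time of Anion Gap Closure (TAGC) will use the ADA definition", that is, AG of 12 mEq/L or less.

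The two groups are found differently. For the intervention group, III.A says: "Screening of patient eligibility and informed consent will be done by the MICU admitting physician once the patient gets admitted to MICU". The intervention paragraph in III.C refers explicitly to the inclusion criteria. Controls are "consecutive adults who admitted to FV-MICU with a diagnosis of DKA in the period between January 1st 2019 till the IRB approval date" who did not "receive basal insulin before AG closure". They are listed through an electronic records request and matched on basal characteristics and DKA severity (III.A). The control paragraph does not mention the inclusion or exclusion lists. Those lists follow under a heading that names both groups, without being assigned to either.

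**The concern.** An entry rule should guarantee that the primary outcome can be measured in everyone who enters. Here it does not. A patient with a DKA code and AG of 12 or less at IV insulin start has already reached the endpoint, so the time to closure is zero or undefined. The plan does not say whether to enter 0 h, exclude the patient or treat the value as missing. That choice would then be made with the control data in hand.

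The control paragraph raises a related question. Read alone, it would admit a control who needed vasopressors, had end-stage renal disease or was transferred in, all of which are grounds for exclusion in III.C. Controls are historical and the tests in section V are unadjusted, so a difference in eligibility between the groups could be mistaken for an effect of early glargine.

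**Working it through.** **Is there another barrier to a closed-gap patient?**

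- Severity matching: the table introduced by "DKA classification as the following table from ADA" grades on glucose, arterial pH and bicarbonate, not on AG. Arterial pH is not among the initial laboratory values to be collected.
- No basal insulin before AG closure (controls): this presupposes an open gap but does not test for one.
- IV insulin continued until closure (III.A): this is a management step, not an entry criterion.
- Live screening: it makes such an enrolment unlikely in the intervention group. No equivalent laboratory check is stated for controls.

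These rules make the case less likely but do not exclude it.

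**The plan's sample size.** Inputs from section V: mean 15.6 h, SD 6 h, 20% difference, one-sided alpha 0.025, beta 0.10. The target is 0.20 × 15.6 = 3.12 h. Then n per group = 2 × 36 × (1.960 + 1.282)² / 3.12² = 77.7, so 78 per group and 156 in total, against 160 stated. The plan's figure reproduces. With 80 per group (an equal split is assumed, as the ratio is not stated), power is 90.8% by the normal approximation and 90% for a simulated t-test.

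**Illustration of size.** Assume that k of the 80 patients in an arm with mean m are entered as 0 h, and let f = k/80. The arm mean becomes m(1 − f), and the variance seen by the test becomes 36(1 − f) + m²f(1 − f). Let SE = √[(sum of the two arm variances)/80]. With k fixed, the sampling SD of the difference is s = √[36{(1 − f_control) + (1 − f_intervention)}/80]. Power = Φ[(difference − 1.96 SE)/s]. The true means are 15.6 h (control) and 12.48 h (intervention).

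| Entered as 0 h | Difference (h) | SE | s | Power, formula | Power, simulated t-test |
|---|---|---|---|---|---|
| none | 3.120 | 0.949 | 0.949 | 90.8% | 90% |
| 2 controls | 2.730 | 0.981 | 0.943 | 80.4% | about 80% |
| 4 controls | 2.340 | 1.011 | 0.937 | 64.9% | about 64% |
| 2 in each arm | 3.042 | 1.000 | 0.937 | 87.6% | about 87% |
| 4 in each arm | 2.964 | 1.045 | 0.925 | 83.9% | about 84% |

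Each control entered as 0 h lowers the control mean by 15.6/80 = 0.195 h, or 6% of the 3.12 h target. With the Mann-Whitney test, which section V allows for non-normal data, 2 or 4 such controls give about 81% or 70%, from 89%.

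With equal numbers in both arms and no true effect, the one-sided type I error is Φ(−1.96 SE/s), where both arms now have m = 15.6. This is about 1.7% for 2 per arm and 1.2% for 4 per arm, below the nominal 2.5%.

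If such controls are dropped instead, SE = 6√[1/(80 − k) + 1/80] and power is 90.5% (k = 2) or 90.1% (k = 4).

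No arithmetic applies to the question of which lists govern controls.

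**The case against.** The strongest reply is that the harm depends on choices the plan never makes. Every loss of power above assumes entry as 0 h. A closed-gap patient has no closure event to record and might simply be dropped, which leaves power near 90%. The large losses also need the problem to sit in one arm only. The documents give no rate of code-only patients. All of this stands, and it limits the figures to illustration.

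A reader might infer that the rule inflates the false-positive rate. That would need closed-gap patients in the intervention arm only: 2 or 4 of 80 entered as 0 h would raise the one-sided error to about 5% or 10% (t-test). The documents do not support expecting this. Intervention patients are screened live by the admitting physician, and the route is more plausible among controls, where it costs power.

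A reader might also infer that the exclusions do not apply to controls. The text does not establish that: the lists sit under a heading that covers both groups and can be read as common. What remains is an ambiguity.

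Nor does the laboratory-only definition that begins "Transitional failure will be defined as the recurrence of DKA" show an inconsistency. Recurrence within 24 hours is an in-stay event that a diagnosis code could not time. It shows only that a laboratory definition is workable here.

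**Conclusion.** The point holds in a limited form. As written, the entry rule admits a code-only patient with AG of 12 or less at IV insulin start, and that patient has no valid primary outcome. Severity matching and the basal-insulin condition reduce the chance without removing it. Separately, the plan should say whether the inclusion and exclusion lists govern controls.

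The size cannot be fixed from the documents. On the assumptions of 80 per arm, SD 6 h and a 3.12 h target, the effect runs from almost none (controls dropped) to a fall in power from 90% to about 64% (4 controls entered as 0 h). The sample size of 160 is not in question, and no estimate of size or direction is possible for the control-criteria ambiguity. The change is worth making before controls are abstracted, because it is cheap and removes a choice that would otherwise be made after the data are seen.

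**What to change.** - Use the ICD-10 codes only to find candidate charts.
- In both groups, require AG above 12 on the last value at or before IV insulin start, and measure time to closure from IV insulin start.
- State in III.C that every chart-verifiable inclusion and exclusion criterion applies identically to controls.
- Add to section VII that capacity and willingness to consent cannot be fully reproduced in retrospective controls.

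The cost is a few sentences of eligibility text and one added field. Initial AG and IV insulin start time are already on the variable list, but the initial laboratory values carry no timing, so the AG needs a draw time and the rule above for choosing the value. Some candidate controls will be lost. No treatment rule changes.
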